IRB Minimal Risk Protocol Template

Note: If this study establishes a human specimen repository (biobank) for research purposes, do not use this template. Use the Mayo Clinic Human Specimen Repository Protocol Template found on the IRB home page under Forms and Procedures at <http://intranet.mayo.edu/charlie/irb/>

First-time Use: Use this template to describe your study for a new IRB submission.

1. Complete the questions that apply to your study.
2. Save an electronic copy of this protocol for future revisions.
3. When completing your IRBe application, you will be asked to upload this document to the protocol section.

Modification: To modify this document after your study has been approved:

1. Open your study in IRBe. Click on the study 'Documents' tab and select the most recent version of the protocol. Save it to your files.
2. Open the saved document and activate "Track Changes".
3. Revise the protocol template to reflect the modification points, save the template to your files
4. Create an IRBe Modification for the study and upload the revised protocol template.

General Study Information

Principal Investigator: [name], Magnetic Resonance Technology and Use Design Lab, Department of Radiology, Mayo Clinic, Rochester

Other Study Staff: [name],
[name]
[name]

Study Title: **Detection of the occurrence of infiltration of gadolinium injection in brain MR scans using artificial intelligence.**

Protocol version number and date: Version 2: January 20th, 2022

Research Question and Aims

Hypothesis: Machine learning can be used to make a binary decision regarding the occurrence of infiltration of the MR contrast agent, gadolinium, through analysis of MR Brain scan images.

Aims, purpose, or objectives: The aim of this study is to *develop* machine-learning algorithms and infrastructure through the analysis of MR image data for training and testing, for the detection of intravenous infiltration of MR contrast agent. This aim will be achieved through the analysis of both non-infiltrated and infiltrated brain MR images. This analysis will involve segmenting and analyzing the nasal mucosa region following contrast agent administration. The developed machine learning model will be trained to be able to differentiate between non-infiltrated (contrast-enhanced) and infiltrated MR images and thus determine if infiltration has occurred. The training and testing data will include both prospective and retrospective MR data.

This IRB application outlines the part of the study which will involve the collection prospective data for training the machine learning model.

Background (*Include relevant experience, gaps in current knowledge, preliminary data, etc.*):

In 2015, an estimated 17 million magnetic resonance imaging (MRI) examinations were performed in the United States using intravenous (IV) contrast agents [1], reflecting the essential role of IV contrast in the detection, characterization, and staging of disease. On occasion, the IV line is inadequate and causes the contrast medium to infiltrate into the muscle tissue in the arm, which can cause discomfort to the patient, delays with the patient scan as well as the need for a repeat exam to be performed or patient call-back, if not detected in a timely manner. The risk of undetected contrast medium extravasation is increased when automated mechanical injectors or higher injection rates are used for the contrast material injection [2-3]. Thus, if the occurrence of IV infiltration could be detected during the patient MR examination before the patient is removed from the scanner this would significantly improve both the patient experience and the clinical workflow. To that end, this study aims to develop a machine learning algorithm to detect intravenous infiltration, into the muscle of MR contrast agent used for routine brain MR examinations, through the analysis of the nasal mucosa.

Study Design and Methods

Methods: *Describe in lay terms, completely detailing the research activities that will be conducted by Mayo Clinic staff under this protocol.*

We will recruit 40 patients presenting for a clinical Magnetic Resonance Imaging (MRI) brain without and with IV contrast agent. Informed written consent will be obtained prior to the participation in the study and recorded in clinical documents. Each patient will be contacted by the principal investigator or one of his/her designees. The potential risks to participants will be minimal. The specific absorption rate (SAR) used in this study is well under the current FDA safety limits for MRI. No additional drugs or invasive procedures will be used in the study.

Medical charts will be abstracted for imaging and pathologic findings. Patients will undergo their one additional MR sequence as part of their clinical MRI brain scan. This additional sequence will be included prior to IV contrast administration as part of the standard MR brain without and with IV contrast examination.

Commercially available MRI scanners (General Electric (GE) Medical Systems, Wauwatosa, WI, USA at both 1.5T and 3T and Siemens, Siemens Healthcare, Germany) will be used.

Study Procedure

Commercially available MRI scanners (General Electric (GE) Medical Systems, Wauwatosa, WI, USA at both 1.5T and 3T and Siemens, Siemens Healthcare, Germany at both 1.5T and 3T) will be used. A total of 40 patients will be recruited and randomly selected from the cohort of patients undergoing a MR brain without and with IV contrast examination on the Siemens 1.5T and 3T, and GE 1.5T and 3T MR scanners within the clinic. The additional sequence will be a sagittal T1 CUBE FS for the GE scanners and a sagittal T1 SPACE FS for the Siemens scanners.

The additional sequence will be anonymized and stored for subsequent analysis using the machine learning model as part of the training phase.

This study involves the development of an AI algorithm which analyze images from routine Brain without and with IV contrast agent (Gadolinium (Gd)) examinations to confirm that Gd contrast agent has been correctly administered. The training and testing data will include both prospective and retrospective MR data. We require additional data which simulates the occurrence of IV infiltration during a routine brain without and with IV contrast exam as currently there is a low number of previous studies (n= 50) with associated MR images demonstrating IV infiltration. The data collected as part of this innovation study will be used to augment the retrospective data already collected for the training and testing of the developed AI algorithm.

The machine learning training and testing process is described below and illustrated in Figure 1.

- i. Training Phase - Predictive machine learning models for detection of infiltration will be developed and the performance optimized. Machine Learning Tasks will be to (a) differentiate nasal mucosa with Gd contrast agent uptake vs. nasal mucosa or eye fat ratio without Gd contrast agent uptake.
- ii. Test Phase - Evaluate the machine learning model and then compare them with the assessment by radiologists using McNemar's test and Receiver Operator Curve (ROC) analysis with specificity threshold equivalent to clinical reporting.

[figure not shown]

Figure 1: (a) Radiomics Machine Learning model development and training workflow. (b) (i) During training, the network weights will be optimized according to the error calculated by the binary loss function; (ii) After each training epoch, the model performance will be assessed by the area under the receiver-operating characteristic curve (AUC) on the validation set; (iii) The parameters of the model predictions will be recalibrated using the unseen calibration dataset and (iv) Model testing will be carried out in the unseen test cohort using the best performing model identified from the validation set and the performance will be evaluated using receiver-operator characteristic curve analysis, net benefit analysis and intra-class correlation coefficient.

Subject Information

Target accrual is the proposed total number of subjects to be included in this study at Mayo Clinic. A "Subject" may include medical records, images, or specimens generated at Mayo Clinic and/or received from external sources.

Target accrual: 40

Subject population (children, adults, groups): Adults undergoing MR brain without and with IV contrast examination as part of their care plan.

Inclusion Criteria:

Patients undergoing a MR brain without and with contrast examination on any GE or Siemens 1.5T and 3T MRI system within Mayo Clinic, Rochester, as part of their care plan.

Exclusion Criteria:

Pregnant Women and individuals under the age of 18 years.

Review of medical records, images, specimens

Check all that apply (data includes medical records, images, specimens).

Only data that exists before the IRB submission date will be collected.

Date Range for Specimens and/or Review of Medical Records:

Note: The Date Range must include the period for collection of baseline data, as well as follow-up data, if applicable.

The study involves data that exist at the time of IRB submission **and** data that will be generated after IRB submission. Include this activity in the Methods section.

Examples

- The study plans to recruit subjects undergoing a MR brain without and with IV contrast examination as part of their care plan.

The study will use data that have been collected under another IRB protocol. Include in the Methods section and enter the IRB number from which the research material will be obtained. *When appropriate, note when subjects have provided consent for future use of their data and/or specimens as described in this protocol.*

Enter one IRB number per line, add more lines as needed

Data Specimens Data & Specimens _____

Data Specimens Data & Specimens _____

Data Specimens Data & Specimens _____

Data Analysis

Power analyses may not be appropriate if this is a feasibility or pilot study, but end-point analysis plans are always appropriate even if only exploratory. Provide all information requested below, or provide justification if not including all of the information.

Power Statement: Not applicable – pilot study

Data Analysis Plan:

Receiver operating characteristic (ROC) curves will be generated for radiologist diagnosis and the machine learning models decisions and compared using the Delong test. Cut-off values for the machine learning models will be selected to match the sensitivity of radiologist clinical assessment in the training cohort, in order to construct working points of the models that maintain clinically achieved detection rates for the specific clinical exams. The sensitivity and specificity of the machine learning models will be compared based on the reduction of false-positive (FP) decisions compared with the clinical reference. The performance of the machine learning models will be compared to that of the radiologist performance using the McNemar test.

Endpoints

Primary: Area-under-curve performance for each machine learning model and the performance measure “net benefit”. Net benefit is defined as:

$$\text{Net benefit} = \frac{\text{True positives}}{\text{Total number of patients}} - \frac{\text{False positives}}{\text{Total number of patients}} \times w$$

The weighting factor, w , corresponds to the odds (i.e. the harm-to-benefit ratio) of the chosen risk threshold. Retest-repeatability of the model determined from intra-class correlation coefficient (ICC).

Secondary: Sensitivity and specificity of each machine learning model and comparison with radiologist performance using the McNemar test.

References

1. OECD Health Statistics. Health care utilisation. OECD. Stat Web site. Available at: http://stats.oecd.org/Index.aspx?DataSetCode=HEALTH_PROC.

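### The only prospective images named as stored for the model are pre-contrast, so the 40 patients feed one class only and class is partly confounded with data source

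*Protocol*

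**What the plan says.** The Protocol's Methods and Study Procedure sections describe what the prospective patients contribute:

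- Number: "A total of 40 patients will be recruited and randomly selected from the cohort of patients" who are having a clinical brain MRI before and after contrast.
- Timing of the research scan: "This additional sequence will be included prior to IV contrast administration as part of the standard MR brain without and with IV contrast examination".
- Type: "The additional sequence will be a sagittal T1 CUBE FS for the GE scanners and a sagittal T1 SPACE FS for the Siemens scanners".
- Purpose: "We require additional data which simulates the occurrence of IV infiltration during a routine brain without and with IV contrast exam", because only 50 earlier studies show a true infiltration.
- Storage: "The additional sequence will be anonymized and stored for subsequent analysis using the machine learning model as part of the training phase".
- Use: "The data collected as part of this innovation study will be used to augment the retrospective data already collected for the training and testing".
- Other data: "Medical charts will be abstracted for imaging and pathologic findings".

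No other image series from these patients is named as stored for the model. The text does not say that their post-contrast images are left out, nor that a study code is or is not kept. It describes no balancing by source and no reporting by source. It does not say which sequences, scanners or dates the retrospective images cover. Under Endpoints, AUC and net benefit are listed as primary.

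**The concern.** The learning task is to tell nasal mucosa that has taken up gadolinium from nasal mucosa that has not. If the prospective patients supply only the second kind, then being a prospective image already identifies the class. Any feature that marks the new series, such as its acquisition period or, if the archive differs, its sequence or scanner, can stand in for absence of uptake.

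A model could use that shortcut in place of the gadolinium signal. If prospective images also enter the test set, the pooled AUC and net benefit would look better than performance on real infiltrations warrants. If they are used for training only, the reported test figures are not inflated in this way, but the model may carry over less well to routine exams, where infiltrated and normal scans come from one protocol.

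Every one of these patients has contrast as part of the ordered exam, so a same-patient, same-scanner comparison image may already exist. Which series are kept, and under what identifier, is settled when data are collected. If anonymisation is irreversible, no later analysis can restore the pairing.

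**Working it through.** The protocol has no sample-size or performance figure to reproduce: its power statement says not applicable because this is a pilot, and 40 is an accrual target. The arithmetic below only illustrates how much source alone could contribute.

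**Inputs from the Protocol**
- Prospective no-uptake images: 40 (Study Procedure).
- Retrospective true infiltrations: 50 (Study Procedure).
- Prospective contrast-enhanced images named as stored: none.
- Retrospective contrast-enhanced images: number not stated.

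**Formula.** Take a classifier that sees only whether an image is prospective and calls every prospective image infiltrated. With one binary feature,

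AUC = 0.5 + (sensitivity − false-positive rate) / 2.

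Sensitivity is the share of no-uptake images that are prospective. The false-positive rate is the share of enhanced images that are prospective.

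**As written, all 40 and all 50 in the evaluated set**
- Sensitivity = 40 / (40 + 50) = 0.444.
- False-positive rate = 0, so specificity is 100%.
- AUC = 0.5 + 0.444 / 2 = 0.722.

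**Testing on retrospective cases only**
- Sensitivity = 0 and false-positive rate = 0, so AUC = 0.500.

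**Dependence on the test mix.** The split is not given. With all 40 prospective images and an assumed smaller number of true cases in the evaluated set:

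| True cases (assumed) | Share simulated | Source-only AUC |
|---|---|---|
| 50 | 0.444 | 0.722 |
| 40 | 0.500 | 0.750 |
| 25 | 0.615 | 0.808 |
| 10 | 0.800 | 0.900 |

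**After pairing.** Suppose each of the 40 also supplies a post-contrast image, and N retrospective enhanced images are in the set (N is an assumption). Within the prospective images, 40 against 40, source carries no information and AUC = 0.500. In the pooled set the false-positive rate becomes 40 / (N + 40):

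| N (assumed) | False-positive rate | Source-only AUC |
|---|---|---|
| 50 | 0.444 | 0.500 |
| 90 | 0.308 | 0.568 |
| 200 | 0.167 | 0.639 |
| 500 | 0.074 | 0.685 |
| 1000 | 0.038 | 0.703 |

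Pairing therefore removes the shortcut inside the prospective data. In the pooled data it does so only when the two classes have the same prospective share.

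**The case against.** Several stronger readings are tempting, and the Protocol does not support them.

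*That no post-contrast series is kept and no link survives.* Both are inferred from silence. The storage sentence governs the added research sequence and does not bar use of the clinical series. Research Question and Aims says that training and testing data include prospective and retrospective images without restricting the prospective ones further. Chart abstraction needs identification at some stage, and its timing relative to anonymisation is not given. Nor is it shown that chart findings must be linked to images for this learning task.

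*That class and source coincide.* They do among the prospective images named, where only one class is named. In the pooled data the 50 retrospective infiltrations share a source with the retrospective enhanced images, so source cannot separate the classes fully. A sequence or scanner mismatch with the archive is an assumption, because the archive is not described.

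*That an AUC near 0.72 is to be expected.* It requires source to be fully recognisable, no gadolinium signal to be learned, no prospective enhanced images, and the 40 to be in the test set. The last is unclear: the storage sentence points to training, while the sentence on augmenting the archive covers training and testing.

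The analysis also works on segmented nasal mucosa and an eye-fat ratio, not on whole images. That may weaken acquisition signatures, though it does not remove them. An eye-fat ratio would itself respond to fat suppression if the archive images were acquired differently.

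Finally, details of data partition are often left to an analysis plan, and this is a pilot. That is fair for the partition rule, but not for which images are stored and under what identifier, which belongs in the study procedure.

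These objections limit the point to partial confounding of uncertain size. They do not remove it: the only prospective series named is still one-class.

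**Conclusion.** The point holds in limited form. As written, the 40 patients contribute only no-uptake images, 40 of 90 (44%) if all are pooled with the 50 true infiltrations, so class is partly confounded with data source and acquisition period. The Protocol leaves open whether the same patients' post-contrast images are used.

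The possible effect on pooled AUC runs from none (source-only AUC 0.50, retrospective test cases only) to about 0.72 (all 40 and all 50 tested, source fully recognisable, no prospective enhanced images). It would be higher if fewer true cases were tested beside the 40. These are bounds on what a shortcut could give under stated assumptions, not predictions of the model's behaviour. The change is worth making before images are stored, since irreversible anonymisation would close off the remedy.

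**What to change.** In Study Procedure, state that:

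1. Each patient's clinically acquired post-contrast series of the same sequence type as the added one, where the exam includes it, is stored together with the added pre-contrast series.
2. Both are held under one study code, coded and not irreversibly anonymised.
3. The two series enter as a within-patient pair (no gadolinium / gadolinium). Only same-sequence pairs are used, because a pair that differs in sequence as well as contrast would build a new confound into the remedy.
4. Each pair stays in one data partition.

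In Data Analysis, add that test performance is reported separately on the true retrospective infiltrations, set against retrospective enhanced images so that both classes share a source. This is needed because pairing alone leaves a source signal in the pooled data unless the classes are balanced by source. Say also whether the prospective images may enter the test set.

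The cost is protocol wording and a key held under IRB approval. No extra scan, contrast or patient time is needed. Patients whose exam has no post-contrast series of the same type would yield no pair, and the Protocol does not show how many that would be.

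### The primary net benefit uses a risk threshold, but predictions are recalibrated to an unspecified study set and nothing ties them to the clinic infiltration rate

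*Protocol*

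**What the plan says.** - **Recalibration.** The caption of Figure 1, item (b)(iii), states: "The parameters of the model predictions will be recalibrated using the unseen calibration dataset". It does not give that set's source, size or infiltrated share.
- **Endpoint.** Endpoints, Primary, names AUC and net benefit. Net benefit is true positives over all patients, minus false positives over all patients times w, where w "corresponds to the odds (i.e. the harm-to-benefit ratio) of the chosen risk threshold". No threshold value is given.
- **Frequency in practice.** The Background says: "On occasion, the IV line is inadequate and causes the contrast medium to infiltrate into the muscle tissue in the arm". No rate is given.
- **Study cases.** Study Procedure reports a "low number of previous studies (n= 50) with associated MR images demonstrating IV infiltration" and continues: "We require additional data which simulates the occurrence of IV infiltration". The protocol recruits 40 patients for one extra sequence. Methods gives its timing: "This additional sequence will be included prior to IV contrast administration".
- **Use of the new scans.** Study Procedure says the extra sequence is "stored for subsequent analysis using the machine learning model as part of the training phase". It also says the collected data will "augment the retrospective data already collected for the training and testing of the developed AI algorithm".
- **Working cut-offs.** The Data Analysis Plan sets the models' cut-offs by matching radiologist sensitivity in the training cohort, not by a risk value.

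**The concern.** Recalibration makes average predicted risk agree with the case share of the set it is fitted on. If that set holds many more infiltrations per exam than the clinic does, a predicted risk of 5% means a much smaller risk at the scanner. Net benefit depends on the scale: using threshold odds as the price of a false positive assumes that an exam sitting at the threshold really carries that risk in the population the tool will serve.

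Two things then go wrong together. A threshold on the study scale flags exams whose clinic risk is far below the one judged worth acting on. And the formula, computed at the study mix, credits true positives at a frequency the clinic will never see. A primary endpoint could look excellent for a model that does net harm in routine use, or lead to rejection of one that is useful once its risks are put on the clinic scale.

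**Working it through.** The protocol states no prevalence, threshold or accuracy figure, so there is no stated result to reproduce. The check asks how large the effect is under labelled assumptions.

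**1. Is enrichment likely?** The case counts come from Study Procedure (50 real infiltrations, 40 patients with a simulating scan). The number of non-infiltrated exams is not given and is varied here.

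| Non-infiltrated exams | Share, 50 real cases only | Share, 50 + 40 |
|---|---|---|
| 90 | 36% | 50% |
| 500 | 9% | 15% |
| 1,000 | 4.8% | 8% |

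A 0.5% share with 50 cases needs 50/0.005 - 50 = 9,950 non-infiltrated exams. Nothing in the protocol suggests a set of that size.

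**2. Shift in the risk scale.** Study odds divided by clinic odds = [s/(1 - s)] / [c/(1 - c)], with s the calibration case share and c the clinic rate. Assumed ranges: s 10% to 50%, c 0.2% to 1%.
- Smallest: (0.10/0.90)/(0.01/0.99) = 11.
- Largest: (0.50/0.50)/(0.002/0.998) = 499.
- Central case, s = 30%, c = 0.5%: (0.30/0.70)/(0.005/0.995) = 85.3.

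With a 5% threshold, w = 0.05/0.95 = 0.0526. In the central case the clinic odds at that cut are 0.0526/85.3 = 0.000617, a true risk of about 0.06%.

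**3. Effect on net benefit.** Assumed score model: equal-variance binormal, AUC 0.96, so d = √2 × Φ⁻¹(0.96) = 2.476. The cut is x = [ln(w / prior odds) + d²/2]/d. Sensitivity is 1 - Φ(x - d) and the false-positive rate (FPR) is 1 - Φ(x). Net benefit at prevalence c is c × Se - (1 - c) × FPR × w.

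| | Study-scale threshold | Clinic-scale threshold |
|---|---|---|
| Cut x | 0.391 | 2.187 |
| Sensitivity | 0.981 | 0.614 |
| FPR | 34.8% | 1.4% |
| Flagged per 1,000 clinic exams | 351 | 17 |
| Net benefit per 1,000 at c = 0.5% | -13.3 | +2.3 |

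- Study scale: 0.005 × 0.981 - 0.995 × 0.348 × 0.0526 = -0.0133.
- Clinic scale: 0.005 × 0.614 - 0.995 × 0.0144 × 0.0526 = +0.0023.
- The study-scale cut evaluated at the study mix: 0.30 × 0.981 - 0.70 × 0.348 × 0.0526 = +0.282, or about +282 per 1,000. This is the figure the plan's formula would report.

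**4. Sensitivity to the assumptions.** With s = 10% and the rest unchanged, FPR is 17.5% and clinic net benefit is -4.5 per 1,000. Over 54 combinations (AUC 0.90 or 0.96; s 10, 30, 50%; c 0.2, 0.5, 1%; threshold 2, 5, 10%), study-scale net benefit at the clinic rate is negative in 52. The two exceptions both have AUC 0.96, s = 10% and c = 1%.

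**5. If the sensitivity-matched cut supplies the counts instead.** Take a matched sensitivity of 0.90 (assumed). Then x = 2.476 - 1.282 = 1.194 and FPR = 11.6%. Recalibration does not move this point, but it is not the point that w = 0.0526 describes. Net benefit is 0.30 × 0.90 - 0.70 × 0.116 × 0.0526 = +0.266 at the study mix and 0.005 × 0.90 - 0.995 × 0.116 × 0.0526 = -0.0016 at the clinic rate. The sign again differs.

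**6. What does not change.** Recalibration is monotone. In a simulated sample of 90 against 90, AUC (0.955) and the sensitivity-matched point (sensitivity 0.90, specificity 0.856) were identical at prevalences of 50% and 0.5%. Only the numerical cut moved, from 0.467 to 0.0044.

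**The case against.** The strongest reply is that no sentence in the protocol classifies exams by a risk threshold. The Data Analysis Plan sets working cut-offs by matching radiologist sensitivity, and the risk threshold enters only through w. A reader might infer from the calculation that the plan as written produces a false-alarm rate near 35% at the scanner. The protocol does not support that: under its stated cut-off rule the operating point is unaffected by recalibration, and no deployment rule is given. This part of the objection stands and confines the point to net benefit and any later use of a risk threshold. It does not rescue net benefit, because a sensitivity-matched cut does not correspond to w (step 5). It is true that, under that reading, weighting the formula to the clinic rate would correct the prevalence without any intercept shift. The mismatch between cut and w would remain.

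A reader might also infer that the calibration set is stated to be rich in infiltrations. It is not. Its mix is undescribed, and one sentence assigns the added scans to training only. Enrichment is a strong inference from the case counts, but still an inference.

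Nor would the model pick out the wrong exams. Ranking is preserved, so a study-scale threshold flags more exams in the same order.

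Finally, this is a pilot, and a statistical analysis plan that is not shown may describe the calibration set and choose the threshold. That excuses the absence of those details. But the protocol itself fixes both the recalibration step and net benefit as a primary endpoint, without tying predicted risk to the clinic.

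**Conclusion.** The point holds for one primary measure. As the protocol stands, the net benefit it would report cannot be read as net benefit in the clinic and could differ from it in sign: -13.3 against +2.3 per 1,000 exams in the central illustration, with about +282 shown at the study mix. AUC is unaffected, and so are sensitivity, specificity and the McNemar comparison at the sensitivity-matched cut-off.

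The size rests on assumptions that are not in the protocol: the calibration case share, the clinic rate, the threshold, the AUC and the binormal score model. If the calibration and test sets were consecutive clinic exams at the natural rate, the concern would disappear. The stated case counts make that unlikely. The change should be made before the test phase, since a primary endpoint is affected and the correction is short.

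**What to change.** In Figure 1 (b)(iii) and Endpoints, for net benefit only:

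1. State the infiltrated share of the calibration and test sets, and a clinic infiltration rate with a low-high range.
2. After recalibration, shift the intercept: logit(p_clinic) = logit(p_calibrated) - [logit(calibration case share) - logit(clinic rate)].
3. Apply the chosen threshold and its w to p_clinic.
4. Compute net benefit as rate × sensitivity - (1 - rate) × FPR × w, using the same clinic rate, and report it across the range.
5. State that this threshold, not the sensitivity-matched cut-off, supplies the true and false positives for net benefit. The sensitivity-matched cut-off stays in place for sensitivity, specificity and McNemar.

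The cost is a few sentences and a rate, with no new data collection if records can supply one. There are two downsides. The clinic rate is uncertain and has to be assumed or taken from records, so the result becomes a range. The shift also assumes that images within each class look the same in the study as in the clinic, which is less certain where pre-contrast scans stand in for real infiltrations. Reporting the result with and without the simulated cases would show how much depends on this.

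### The DeLong comparison of radiologist and model is a fair AUC comparison only with a graded reader score, which the protocol does not describe; with a yes/no read, a continuous model score and an independent reference standard it tends to favour the model

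*Protocol*

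**What the plan says.** The protocol's Data Analysis Plan fixes the test: "Receiver operating characteristic (ROC) curves will be generated for radiologist diagnosis and the machine learning models decisions and compared using the Delong test".

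On the **radiologist**, the same section chooses model cut-offs to "match the sensitivity of radiologist clinical assessment" in the training cohort. Study Procedure, item ii (Test Phase) refers instead to a "specificity threshold equivalent to clinical reporting". The secondary endpoint adds a "comparison with radiologist performance using the McNemar test", which needs yes/no calls. No rating scale or confidence score is mentioned.

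On the **model**, the Figure 1 legend has AUC assessed after every training epoch and says "The parameters of the model predictions will be recalibrated using the unseen calibration dataset". With selectable cut-offs, this points to a continuous score. The hypothesis points the other way: "Machine learning can be used to make a binary decision regarding the occurrence of infiltration". The DeLong sentence itself also speaks of the models' decisions.

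On the **reference standard**, the Data Analysis Plan mentions a clinical reference and does not say how it is obtained.

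Under Endpoints, the primary measures are each model's own AUC and net benefit, together with retest repeatability by ICC. The difference in AUC between radiologist and model is not listed. The power statement is marked not applicable because this is a pilot.

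**The concern.** DeLong compares two areas under empirical ROC curves. The comparison is like with like only if both sides are recorded on scales of similar fineness. A yes/no read gives one point joined by straight lines to the two corners, and that area is smaller than the area under the concave curve on which the reader actually operates. A continuous score from an equally accurate model gets credit for the whole curve.

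A significant result in favour of the model could then come from the recording format rather than from better detection. Such a result would be easy to report as the model outperforming radiologists, and the planned sentence gives no safeguard against it.

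**Working it through.** The protocol gives no AUC, reader cut, correlation between reader and model, or test-set size, so there is no figure of its own to reproduce. Every input below is an assumption except the count of infiltrated studies.

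**Inputs**
- True AUC 0.90, 0.95 or 0.99, identical for radiologist and model; binormal curve with equal variances.
- Reader cut midway between the two class means, unless stated otherwise.
- Latent correlation between reader and model 0.3 and 0.6.
- Truth labels independent of the radiologist.
- Test sets with 10 or 20 infiltrated cases. The Study Procedure says "currently there is a low number of previous studies (n= 50) with associated MR images demonstrating IV infiltration", and these must also serve training, validation and calibration.

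**Step 1: size of the understatement.** The separation is d = √2 × Φ⁻¹(AUC). At the midpoint cut, sensitivity = specificity = Φ(d/2), so the one-point AUC, (Se + Sp)/2, is also Φ(d/2).

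| True AUC | d | One-point AUC | Understated by |
|---|---|---|---|
| 0.90 | 1.812 | 0.818 | 0.082 |
| 0.95 | 2.326 | 0.878 | 0.072 |
| 0.99 | 3.290 | 0.950 | 0.040 |

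Away from the midpoint the gap can be larger. At true AUC 0.90 with Se 0.95 and Sp 0.567, the one-point AUC is (0.95 + 0.567)/2 = 0.758, a gap of 0.142.

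**Step 2: effect on the test.** Paired DeLong simulation at equal true accuracy, 4,000 runs per setting, rejecting at |z| > 1.96 (nominal 2.5% on each side). Entries are the rate of declaring the model better, across the two correlations.

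| Infiltrated / non-infiltrated | AUC 0.90 | AUC 0.95 | AUC 0.99 |
|---|---|---|---|
| 10 / 10 | 12.8–15.0% | 9.9–10.0% | 1.8–2.1% |
| 20 / 20 | 23.1–27.5% | 23.4–26.6% | 8.4–9.3% |
| 10 / 50 | 23.0–27.8% | 22.1–26.1% | 8.6–10.5% |
| 20 / 100 | 34.5–46.9% | 40.5–54.5% | 25.3–31.9% |

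The radiologist was declared better in at most 0.2% of runs. A repeat with fresh random numbers agreed within simulation error. With the reader's specificity set at 0.95 instead of the midpoint, the rates were 1.8–35.9% with 10 per class and 9.0–63.4% with 20 per class.

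**Step 3: controls at the midpoint cut.**
- Both sides binary: at most about 4% on each side, so no material bias. The statistic is then a difference in balanced accuracy, not in AUC over the whole curve.
- Five-level read against a continuous score: model declared better in 0–6% of runs, AUC gap 0.005–0.019.
- Three-level read: 0–9% with 10 to 20 per class, up to 14.5% with 20 and 100, gap 0.013–0.038.

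The controls show that the mismatch of scales produces the excess, not DeLong as such.

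**The case against.** The strongest reply is that the protocol never says the read is yes/no. Planning an ROC curve for radiologists may itself imply a graded rating. One sensitivity to match and a McNemar test are both compatible with a graded read that is later dichotomised, and a statistical analysis plan that is not shown could define the scale. This stands: the yes/no read is an inference. But the comparator is tied to clinical assessment and clinical reporting, and neither is described as graded.

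Secondly, on a literal reading the models' decisions are binary too, and the bias vanishes. This also stands, although recalibrated predictions and selectable cut-offs make a continuous score the more natural reading.

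Thirdly, the direction of the bias depends on truth labels independent of the radiologist. If the labels come from the clinical radiology report, the radiologist's AUC is 1 by construction and DeLong cannot favour the model. The protocol does not rule this out, so the direction is conditional.

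A reader might infer that the plan is bound to declare the model superior, or that its endpoints are compromised. The documents support neither. The first needs three conditions that the protocol does not state. The second fails because each model's own AUC, net benefit, ICC and the McNemar comparison do not use the DeLong result.

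**Conclusion.** The point holds conditionally. As written, the DeLong test against radiologists is an approximately fair AUC comparison only with a graded reader score of about five levels and a continuous model score, and the protocol describes no such reader score. With a yes/no read, a continuous model score and an independent reference standard, the radiologist's AUC is understated by about 0.04 to 0.08 at a midpoint cut. The false rate in favour of the model then runs from about nominal (true AUC 0.99, 10 per class) to roughly 50% (20 infiltrated and 100 non-infiltrated). These figures rest on assumed accuracy, cut, correlation and test-set size, and should be read as a range rather than a prediction for this study.

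The consequence is limited to one comparison that is not a listed endpoint, in a pilot. It is worth correcting because the sentence names a specific test and the material for a better comparison is already planned.

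**What to change.** 1. Restrict DeLong to comparisons between models.
2. Compare model and radiologist in the test set at the cut-off fixed beforehand from the training cohort. Report the paired differences in sensitivity **and** in specificity with confidence intervals, because a match in training need not carry over to the test set. Run McNemar separately in infiltrated and non-infiltrated cases.
3. Label these results descriptive. Under the same assumptions, the Wald 95% half-width for the paired sensitivity difference is 0.16–0.31 with 10 infiltrated cases and 0.12–0.22 with 20. An exact McNemar test of sensitivity 0.80 against 0.95 with independent reads would succeed in under 1% of studies with 10 cases and about 9% with 20.
4. Reconcile the Test Phase text, which uses a specificity threshold, with the Data Analysis Plan, which matches sensitivity, so that one rule sets the cut-off.
5. Keep DeLong against radiologists only if a graded reader score is already planned. In that case state the scale, preferably five or more levels, and enter the model as its continuous score.

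Items 1 to 3 change wording and reporting only, since the cut-off and McNemar are already planned. Item 4 needs a decision as well as an edit. Item 5 costs nothing if graded reads are planned; if the comparator is the existing clinical report, it would need a new read.
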